2.1. Purpose of the Analyses

These analyses will assess the efficacy and safety of repeated doses of LACTIN-V in comparison with the placebo and will be included in the clinical study report.

3. STUDY OBJECTIVES AND ENDPOINTS

3.1. Study Objectives

3.1.1. Primary Objectives

1. To estimate the efficacy of repeated doses of LACTIN-V (2×10^9 cfu/dose) as compared to placebo in preventing BV recurrence by 12 weeks following treatment of BV with MetroGel.
2. To assess the safety of LACTIN-V over 24 weeks by comparing the incidence of adverse events (AEs) between individuals randomized to LACTIN-V or placebo.

3.1.2. Secondary Objectives

1. To investigate the colonization of LACTIN-V (presence of *L. crispatus* CTV-05 in the vaginal specimen) and fluctuations over 12 weeks, in relation to menses and sexual intercourse.
2. To evaluate user acceptability and tolerability of LACTIN-V over 12 weeks, including perceptions around method of delivery and dosing.
3. To measure long-term colonization of LACTIN-V at 24 weeks (12 weeks after last dosing).
4. To estimate the long-term efficacy of repeated doses of LACTIN-V (2×10^9 cfu/dose) as compared to placebo in preventing BV recurrence at 24 weeks (12 weeks after last dosing).

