3.2.3. Secondary Outcome Measures

1. The proportion of subjects experiencing successful colonization with *L. crispatus* CTV-05 following dose of study product through Visit 4 (Week 12, Day 84) in the LACTIN-V arm, overall and by occurrence of menses and intercourse.
2. (*Acceptability of LACTIN-V and the applicator*): The proportion of subjects who are compliant with the complete dose regimen in each study arm as assessed by subject reporting and applicator staining.
3. (*Tolerability of LACTIN-V and the applicator*): The proportion of subjects who discontinue study product early in each study arm due to adverse events.

-
4. (*Acceptability of LACTIN-V and the applicator*): Self-administered questionnaires about acceptability of the study product in each study arm.
 5. The proportion of subjects experiencing successful colonization with *L. crispatus* CTV-05 following dose of study product at Visit 7 (Week 24, Day 168) in the LACTIN-V arm, overall and by occurrence of menses and intercourse.
 6. The proportion of subjects with a positive BV diagnosis in each study arm by Visit 7 (Week 24, Day 168).

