Follow-up visits are scheduled 4, 8, 12, and 24 weeks after enrollment. A memory aid to gauge symptoms and AEs will be reviewed, a questionnaire to collect clinical, including AEs, data will be administered and a pelvic exam will be performed to detect genital tract AEs. Vaginal swabs for wet mount evaluation (Amsel criteria) and Gram stain evaluation (Nugent score) will be collected. A vaginal swab for *L. crispatus* (including CTV-05) identification will be collected. Vaginal applicators will be collected at Visits 2, 3, and 4 and stained with Trypan Blue upon return to the site as a proxy for product use. Telephone interviews will be scheduled between the 12 and 24 week visits, at 16 and 20 weeks after enrollment. [Table 2](#) presents the schedule of events for each visit.

The DSMB met on 02JUN2017 after one-third of the 228 subjects completed Study Visit 2 (Week 4) to review aggregate safety data for increased rate of occurrence of serious suspected adverse reactions. The DSMB will also meet annually to assess safety data on each arm of the study. There are no formal planned interim analyses of efficacy.

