6.1.1. Pseudo Code

The following SAS® pseudo code will be used to calculate the following:

Chi-Square test at 5% two-sided significance level and odds ratio (and 95% asymptotic CI) from 2x2 table:

```
proc freq;
  Table treatment*analysis_variable / chisq;
  ods output ChiSq=outputdsn1;
  ods output RelativeRisks=outputdsn2;
run;
```

Fisher's Exact test at 5% two-sided significance level:

```
proc freq;
  Table treatment*analysis_variable / exact;
  ods output FishersExact=outputdsn;
run;
```

95% Wilson CI for proportions/percentages:

```
proc freq;
  Table treatment*analysisvariable / binomial(wilson);
  ods output binomialcls=outputdsn;
run;
```

95% Wilson CI for difference in proportions (produces Newcombe CI):

```
proc freq;  
  Table treatment*analysisvariable / riskdiff(cl=Wilson);  
  Exact Riskdiff;  
  ods output pdiffcls=outputdsn;  
run;
```

95% Exact Blaker CI for proportions/percentages:

```
proc freq;  
  Table treatment*analysisvariable / binomial(blaker);  
  ods output binomialcls=outputdsn;  
run;
```

Time to event analysis to estimate number of events, median (and other quartiles) time to event, and Kaplan-Meier curves:

```
ods output CensoredSummary =_censorsum Quartiles =_quartiles;  
proc lifetest plots=survival;  
  time studyday*eventstatus(0);  
  strata treatment;  
run;
```

Poisson regression analysis to estimate event rate in each treatment group and rate ratio between treatment groups (with associated 95% CIs):

```
proc genmod;  
  class treatment;  
  model eventcount = treatment / dist=poisson link=log offset=logfollowuptime;  
  lsmeans treatment / ilink diff cl;  
run;
```

Repeated measures logistic regression analysis using Generalized Estimating Equations to estimate odds of event in each treatment group and odds ratio between treatment groups (with associated 95% CIs):

```
proc genmod;  
  class subjectid treatment other_covariates / param=glm;  
  model outcome=treatment other_covariates / dist=bin;  
  repeated subject=subjectid / type=ind/un/exch/ar(1);  
  lsmeans treatment / ilink exp diff cl;  
run;
```

Smoothing spline regression with different curves for each treatment group (with 95% confidence bands):

```
proc transreg;  
  model identity(outcome) = class(treatment / zero=none) | spline(day / knots=0 to  
  max_day by 1);  
run;
```

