6.4. Covariates and Subgroups

The protocol does not define any formal subgroup hypothesis tests, and the study is not adequately powered to perform formal subgroup hypothesis testing. However, safety and enrollment summaries will be presented by clinical site. In addition, summaries of colonization will be presented by subgroups defined by menses and sexual intercourse variables (see Section 8.2).

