Table 21 will present the proportion of subjects who experience successful *L. crispatus* colonization at any time post-baseline through Visit 4 (Week 12) (and 95% Wilson confidence interval) in each treatment group along with the odds ratio of *L. crispatus* colonization (and 95% asymptotic confidence interval). A formal hypothesis test will be performed with null hypothesis that the proportion subjects who experience successful *L. crispatus* colonization through Visit 4 (Week 12) in the LACTIN-V group is equal to that in the placebo group and alternative hypothesis that they are not equal. The p-value from the Chi-Square test will be presented. The analyses will be performed in the ITT, mITT, CC, and PP populations, where the ITT and mITT summaries will use the imputation methods described in Section 6.5. Table 22 presents the same summaries for successful *L. crispatus* colonization at Visit 7 (Week 24). Table 23, Table 24, Table 25, and Table 26 present *L. crispatus* colonization by study visit (and 95% Wilson confidence interval) in each treatment group along with the odds ratio of *L. crispatus* colonization (and 95% asymptotic confidence interval). A formal hypothesis test will be performed with null hypothesis that the proportion of subjects who experience successful *L. crispatus* colonization through each visit in the LACTIN-V group is equal to that in the placebo group and alternative hypothesis that they are not equal. The p-value from the Chi-Square test will be presented. Table 27, Table 28, Table 29, and Table 30 presents summary statistics of the concentration of *L. crispatus* CTV-05 by study visit.

Table 31, Table 32, Table 33, and Table 34 will present *L. crispatus* colonization by study day, treatment group, and number of condom-less sexual intercourse acts for each analysis population. The proportion of subjects with colonization along with the 95% Wilson confidence intervals will also be presented. Number of condom-less sexual intercourse acts will be broken up by quartiles from data obtained from the sexual history interview. If the distribution of sexual intercourse acts is such that the use of quartiles does not lead to distinct intervals of values, other cutpoints will be examined (e.g. tertiles, above/below median). Figure 10, Figure 11, Figure 12, and Figure 13 will present *L. crispatus* CTV-05 concentration by study visit, treatment group, number of condom-less sexual intercourse acts, and analysis population.

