Table 35, Table 36, Table 37, and Table 38 will present *L. crispatus* colonization by study day, treatment group, and number of partners for each analysis population. Number of partners will be categorized as “No partners,” “1 Partner,” and “>1 Partner” from data obtained from the sexual history interview. Depending on the distribution of number of partners, other cutpoints may be examined. Figure 14, Figure 15, Figure 16, and Figure 17 will present *L. crispatus* CTV-05 concentration by study visit, treatment group, number of partners, and analysis population.

Summaries of days since last dose (mean, median, standard deviation, range) will be presented by *L. crispatus* colonization status will be presented in Table 39, Table 40, Table 41, and Table 42. *L. crispatus* CTV-05 concentration and time since last dose will be presented graphically for each visit, treatment group, and analysis population in Figure 6, Figure 7, Figure 8, and Figure 9. A smoothing spline regression model will be fit with treatment group as an independent variable. The fitted curves with 95% confidence bands will be included in the figures. Model fit and inference of the parameters will be commented on in the final report but not included in a table.

L. crispatus colonization will be presented by treatment compliance status in Table 43, Table 44, and Table 45. Treatment compliance will be categorized as “Compliant” or “Not compliant,” and will be assessed from the start of treatment administration up until the visit listed. See Section 9.2 for measurements of

treatment compliance. Box plots of *L. crispatus* CTV-05 concentration by treatment compliance status are provided for each treatment group, visit, and analysis population in [Figure 18](#), [Figure 19](#), and [Figure 20](#).

Summaries of days since the last day of the last menstrual period (mean, median, standard deviation, range) by *L. crispatus* colonization status will be presented in [Table 46](#), [Table 47](#), [Table 48](#), and [Table 49](#).

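### Secondary Objective 1 asks how colonization fluctuates with menses and intercourse, but no planned analysis estimates loss, regain or persistence within a woman, or ties change to either exposure

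*SAP*

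**What the plan says.** The objective appears in Protocol 3.1.2 and SAP 3.1.2: colonization "and fluctuations over 12 weeks, in relation to menses and sexual intercourse". The matching outcome measure in SAP 3.2.3 is a proportion colonized through Visit 4 in the LACTIN-V arm, "overall and by occurrence of menses and intercourse".

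SAP 4.1 sets the sampling times: "Follow-up visits are scheduled 4, 8, 12, and 24 weeks after enrollment". A swab for CTV-05 is taken at each, so a woman who attends has three results within 12 weeks and a fourth at Week 24.

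SAP 8.2 then plans these analyses:

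- Table 21 counts "colonization at any time post-baseline through Visit 4 (Week 12").
- Tables 31-34 give "colonization by study day, treatment group, and number of condom-less sexual intercourse acts for each analysis population".
- Tables 35-38 give "colonization by study day, treatment group, and number of partners for each analysis population".
- Tables 46-49 summarize days since the last period by colonization status at each visit. Tables 50-53 split each visit by whether menses occurred after the last dose.
- Table 54 and Figures 4-5 give Kaplan-Meier estimates of time to first colonization, by arm.

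SAP 6.1.1 holds code for "Repeated measures logistic regression analysis using Generalized Estimating Equations to estimate odds of event in each treatment group". SAP 8.3 applies that model to BV diagnosis and not to colonization. SAP Section 10 says that nothing further is planned.

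**The concern.** Fluctuation is change over time in the same woman. A proportion at each visit shows how many women are colonized, but not whether they are the same women. With stable proportions, the trial could not readily tell lasting colonization from colonization that comes and goes.

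The link to menses and intercourse is weaker still. A cross-tabulation at one visit compares different women. It does not ask whether a woman who was colonized lost the organism after menses or intercourse. The objective would then be reported on without its question being answered, although the swabs and the exposure data are collected.

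**Working it through.** **1. What each colonization output can show.** The documents give no sample size or precision for this objective. The 228 in SAP Section 5 is for BV recurrence. It reproduces (204 completers / 0.9 = 227), but it has no bearing here.

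| Output | Content | Links swabs within a woman | Menses or intercourse |
|---|---|---|---|
| Table 21 | Ever colonized through Visit 4 | Yes, any positive | No |
| Tables 23-30 | Colonization or CTV-05 concentration by visit | No | No |
| Tables 31-38, Figures 10-17 | By condomless acts or partners, each visit | No | Intercourse |
| Tables 46-53, Figures 21-28 | By menses, each visit | No | Menses |
| Table 54, Figures 4-5 | Time to first colonization | Yes, first gain only | No |

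No row has both properties, and no row shows loss. The splines in Figures 21-24 contain treatment and day but no subject term (SAP 6.1.1). The cumulative proportion in Table 21 is broken down only by race (Table 71). Listing 6 shows each woman's results by day, but it is a listing and not an estimate.

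**2. How much is left open.** Assume complete data, 60% colonized at each of Visits 2, 3 and 4, and 80% ever colonized. Both percentages are illustrative. Let a1, a2, a3 be the shares positive at exactly one, two and three visits.

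- a1 + a2 + a3 = 0.80
- a1 + 2·a2 + 3·a3 = 3 × 0.60 = 1.80
- Subtracting: a2 + 2·a3 = 1.00

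The largest a3 has a2 = 0, so a3 = 0.50 and a1 = 0.30. The smallest has a1 = 0, so a3 = 0.20 and a2 = 0.60. Sustained colonization lies between 20% and 50%.

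**3. What the Kaplan-Meier curve adds.** Let u be the share first colonized by Visit 3. Then:

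- Positive at both Visits 2 and 3: 1.2 − u.
- Positive at exactly one of them: 2(u − 0.6).
- Positive at Visit 4 and at least once before: 0.6 − (0.8 − u) = u − 0.2.

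So a3 lies between (u − 0.2) − 2(u − 0.6) = 1.0 − u and the smaller of 1.2 − u and u − 0.2.

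- u = 0.70: 30% to 50%.
- u = 0.80: 20% to 40%.
- u = 0.60 (no new colonization at Visit 3): exactly 40%.

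The curve narrows the range and settles it only in the extreme case. A reader would also have to work this back from outputs whose denominators differ once visits are missed.

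**4. Precision from using three visits together.** On a linear scale with exchangeable within-woman correlation ρ (assumed), the standard error relative to one visit is √((1 + 2ρ)/3) for an exposure that is constant within a woman. That is 0.73 at ρ = 0.3 and 0.86 at ρ = 0.6, a reduction of 14% to 27%. If the exposure varied independently between visits, the ratio would be √((1 − ρ)(1 + 2ρ)/(3(1 + ρ))), from 0.56 at ρ = 0.2 to 0.31 at ρ = 0.8. Visits are about four weeks apart in mostly regularly cycling women, so days since menses may vary little within a woman. The smaller gain is the safer expectation.

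**5. Size of a loss model.** The LACTIN-V arm has 228 × 2/3 = 152 women, and 152 × 0.9 ≈ 137 after the SAP's 10% drop-out. At 60% colonized, about 137 × 0.6 ≈ 82 women are at risk of loss at each of two transitions (Visit 2 to 3, Visit 3 to 4), or 164 records. The number of losses among them is unknown.

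**The case against.** The strongest reply is that the plan meets its own outcome measure. The objective is to investigate, and the measure is a proportion. Protocol 11.6.4.2 promises overall and stratified proportions with standard errors in the LACTIN-V arm across time, with no test or model. SAP 6.4 says that the study is not powered for subgroup testing. By-visit stratified proportions are a fair reading of that text. This stands as a defence of the outcome measure, but the shortfall is against the objective, which names fluctuation.

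A second reply concerns interpretation. Product is used twice weekly through Week 11, so a positive swab at Visit 2 or 3 may reflect a recent dose, and loss or regain between swabs four weeks apart is hard to read. This stands too. It is why a model needs days since last dose, which the SAP already summarizes in Tables 39-42.

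A third reply is that a simple model would not help. Eligibility requires regular cycles or contraceptive amenorrhea, so a covariate for any menses since the previous visit would mainly separate cycling from amenorrheic women. A model of prevalence without prior status would not address loss. Both points stand and shape the fix.

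A reader might go further and infer that the SAP never links a woman's successive swabs. It does: Table 54 and Figures 4-5 date first colonization from her first positive swab and the previous observed time point, so first gain is shown.

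**Conclusion.** The point holds in this form: no planned analysis estimates loss, regain or persistence of colonization within a woman, and none ties change in colonization to menses or intercourse. This follows from SAP 8.2, 8.3 and Section 10 and needs no assumption.

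The 20% to 50% range is an illustration. It rests on the assumed 60% and 80% and on complete data, and the planned Kaplan-Meier curve would usually narrow it. A reader might be tempted to use 61% and 78% from the Phase II-a trial as the per-visit and ever-colonized rates. Protocol 2.1 does not support that: they are the intent-to-treat and according-to-protocol rates for the same four-week outcome.

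This is a worthwhile, inexpensive improvement to a secondary objective. It does not affect the primary efficacy or safety result.

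**What to change.** In SAP 8.2, for the LACTIN-V arm:

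1. Add one table of each woman's colonization sequence over Visits 2-4, classed as sustained, gained, lost, intermittent or never. Add the proportion still colonized at Visit 7 among those colonized at Visit 4.
2. As a supporting analysis, fit one GEE logistic model with the SAP 6.1.1 code, without the treatment term. The outcome is colonization at Visits 2-4, clustered by subject, with robust standard errors and a stated working correlation. Covariates are visit, one of the SAP's existing menses measures chosen in advance (days since the last menstrual period, or menses since last dose), condomless acts since the previous visit, and days since last dose.
3. To address loss, also fit the model conditional on colonization at the prior visit.

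Keep the existing tables and figures. The cost is one table and a short programming task on data already planned for collection. The loss model will be imprecise, so it should be presented as supporting and descriptive.

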3.1.3. Exploratory Objectives

1. To estimate the efficacy of repeated doses of LACTIN-V (2×10^9 cfu/dose) as compared to placebo in preventing repeated (more than one) episodes of BV recurrence up to 12 weeks following treatment of BV with MetroGel.

3.2. Endpoints

3.2.1. Primary Efficacy Outcome Measure

1. The proportion of subjects with a positive BV diagnosis in each study arm by Visit 4 (Week 12, Day 84).

3.2.2. Primary Safety Outcome Measure

1. The proportion of subjects reporting product-related AEs and SAEs in each study arm through Visit 7 (Week 24, Day 168).

3.2.3. Secondary Outcome Measures

1. The proportion of subjects experiencing successful colonization with *L. crispatus* CTV-05 following dose of study product through Visit 4 (Week 12, Day 84) in the LACTIN-V arm, overall and by occurrence of menses and intercourse.
2. (*Acceptability of LACTIN-V and the applicator*): The proportion of subjects who are compliant with the complete dose regimen in each study arm as assessed by subject reporting and applicator staining.
3. (*Tolerability of LACTIN-V and the applicator*): The proportion of subjects who discontinue study product early in each study arm due to adverse events.

-
4. (*Acceptability of LACTIN-V and the applicator*): Self-administered questionnaires about acceptability of the study product in each study arm.
 5. The proportion of subjects experiencing successful colonization with *L. crispatus* CTV-05 following dose of study product at Visit 7 (Week 24, Day 168) in the LACTIN-V arm, overall and by occurrence of menses and intercourse.
 6. The proportion of subjects with a positive BV diagnosis in each study arm by Visit 7 (Week 24, Day 168).

3.2.4. Exploratory Outcome Measures

1. The number of BV recurrences per 12 weeks of follow-up.
2. The probability of BV recurrence during the 12 weeks of follow-up.

3.3. Study Definitions and Derived Variables

3.3.1. BV Diagnosis

The Amsel criteria and Nugent score will be used to diagnose BV.

During a pelvic examination, presence of the following Amsel criteria will be determined:

- a. Homogeneous, thin, grayish-white discharge that smoothly coats the vaginal walls
- b. Vaginal pH > 4.5
- c. Positive whiff-amine test, defined as the presence of a fishy odor when a drop of 10% potassium hydroxide (KOH) is added to a sample of vaginal discharge
- d. Presence of clue cells (>20%) on microscopy

A vaginal swab for assessment of BV by Nugent criteria will be performed. The Nugent score utilized a 0-10-point scale for evaluation of vaginal flora. The Nugent score is interpreted as follows:

- 0-3 Normal
- 4-6 Intermediate
- 7-10 BV

A positive diagnosis of BV is defined by the presence of at least three of the Amsel criteria and a Nugent score of 4 or greater.

3.3.2. Recurrent BV

By standard definition, a treatment of BV is only considered to have failed if Amsel criteria or Nugent score on Gram stain diagnose BV to persist at 22-30 days after the initiation of the antibiotic treatment. As a result, women who continue to have BV during the enrollment visit will not be re-treated with MetroGel at the time of enrollment, as additional time is needed for BV to resolve after antibiotic treatment. Thus, they are not considered treatment failures at this time (approximately 2 days after termination of antibiotic treatment). All BV diagnoses following enrollment are considered incident, as they occur at least 22-30 days after the commencement of MetroGel treatment and consequently are treatment failures or new infections. And so, a positive diagnosis of BV at any visit after the enrollment visit will be considered a recurrence of BV (i.e. there

is no distinction between treatment failure and new infection). A positive diagnosis of BV at the enrollment visit will not be considered a recurrence of BV.

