 - b. Speculum insertion and examination of vagina, fornices and cervix with naked eye. Water will be used to ease speculum insertion. No lubricant should be used as it could contain chlorhexidine which may kill *Lactobacillus*.
 - c. Vaginal pH
 - d. Vaginal swab for wet mount taken from the posterior fornix for yeast vaginitis and clue cells and for amine test (whiff test)
 - e. Vaginal swab for Gram stain (Nugent scoring system)
 - f. Vaginal swabs (no more than two) for storage and future identification of vaginal bacteria, and possible multiomic (e.g. proteomics, metabolomics, etc.) testing
 - g. Vaginal swabs for *L. crispatus* identification with qPCR
If indicated, cervical (or vaginal) swabs for nucleic acid amplification of *N. gonorrhoeae*, *C. trachomatis*, and *T. vaginalis*
Women with findings on pelvic exam at the enrollment visit, including active genital herpes lesions or for other reasons will be considered screening failures, will not be enrolled and will be referred for further evaluation.
5. If indicated, clean catch urine dipstick; urinalysis if abnormal results indicate
6. Rapid urine β hCG pregnancy test. If the test is positive, the enrollment visit will be terminated as the woman is not eligible.
7. All clinical and laboratory findings at the time of the evaluation will be recorded on the CRF. These findings will include observations present on the pelvic exam such as genital findings including location; presence or absence, and character of vaginal or cervical discharge or lesions; and results of any on-site tests.
8. If the clinician suspects the participant developed an STI since the screening visit, appropriate tests will be conducted and if needed the woman will be referred to standard of care treatment in compliance with current CDC STD Treatment Guidelines. The participant cannot be enrolled at this time but could be invited for rescreening after completion of treatment, if indicated.
9. Randomization and enrollment into AdvantageEDCSM
10. LACTIN-V/placebo and applicator will be dispensed to participants. Participants will self-administer the first dose of LACTIN-V/placebo in the clinic during this visit. Participants will then be instructed to administer one dose of LACTIN-V/or placebo once a day at bedtime for the next 4 days (beginning on Day 2) and then twice weekly for 10 weeks. Participants will be instructed to transport the pre-filled applicators while avoiding exposure to high temperatures.

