3.3.4. Baseline Value

The baseline value for most variables will be defined as the last value obtained prior to the first dose of LACTIN-V or placebo. As noted in Section 3.3.2, for BV recurrence, the baseline BV diagnosis will be the diagnosis at the screening visit.

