5. SAMPLE SIZE CONSIDERATIONS

Sample size calculations are based on the assumption of detecting a 50% reduction in the cumulative proportion of subjects who experience BV recurrence by 12 weeks post-administration of study product among subjects receiving LACTIN-V compared to those receiving placebo in a complete case analysis at the 0.05 significance level. The proportion of subjects among controls who will experience BV recurrence at 12 weeks is assumed to be 30%. We assume a LACTIN-V to placebo allocation ratio of 2:1 and 10% of subjects drop-out from the Complete Case population. Given logistical and feasibility constraints on the sample size and that this is a Phase II-b trial, which will provide screening evidence about safety and efficacy for a subsequent Phase III trial, this trial is powered at the 70% level. Given the assumptions above, a sample size of 228 subjects is required to detect a 50% reduction in the cumulative proportion of subjects experiencing recurrence in the Complete Case population with 70% power using the Pearson Chi-Square test.

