6. GENERAL STATISTICAL CONSIDERATIONS

6.1. General Principles

Tabulations will be used extensively to summarize the data. All continuous variables will be summarized using the following descriptive statistics: n (sample size), mean, standard deviation, median, maximum, and minimum. The frequency and percentages (based on the sample size) of observed levels will be reported for all categorical measures. Wilson confidence intervals for binomial proportions and differences in binomial proportions will be computed for efficacy variables. Blaker confidence intervals for binomial proportions and differences in binomial proportions will be computed for safety variables. For the hypothesis tests comparing treatment groups with respect to safety outcomes, the two-sided Fisher's Exact test will be used. For the hypothesis tests comparing treatment groups with respect to efficacy outcomes, the two-sided Chi-Square test will be used. For all tests, a 5% two-sided significance level will be used.

For all efficacy outcome measures, the Complete Case population (see Section 6.3) will be used as the primary analysis population and the Per Protocol, modified Intent-to-Treat, and Intent-to-Treat populations will be used as secondary analysis populations. For all safety analyses, the Safety population will be used as the analysis population.

All summary tables will be structured with a column/sub-table for each treatment group (LACTIN-V, Placebo, and All Subjects). In general, all data will be listed by treatment group and/or subject, and when appropriate by visit number within subject. The total population size relevant to that table/column if applicable, including any missing observations will be displayed in the tables.

Note that in the data listings, Subject ID is the unique subject identifier, not the Study ID used on study and dates will not be included, only Study Day. Study Day 1 will be the day of the first dose of treatment.

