6.7. Multicenter Studies

Safety and efficacy data will be pooled across all clinical sites. Center effects are not anticipated because treatment is self-administered, the sites are using standardized procedures for assessment of unsolicited adverse events, and the study relies on a central laboratory for Gram stain Nugent scoring. See Sections 8 and 9 for more details.

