8. EFFICACY EVALUATION

8.1. Primary Efficacy Analysis

For the primary analysis, the cumulative proportion of BV recurrence by Visit 4 (Week 12) will be summarized by treatment group. A formal hypothesis test will be performed with null hypothesis that the cumulative proportion of BV recurrence by Visit 4 (Week 12) in the LACTIN-V group is equal to that in the placebo group and alternative hypothesis that they are not equal. Cumulative proportion of BV recurrence is defined as follows: the numerator is the number of subjects who experience recurrence at least once through Visit 4 in the particular analysis population and the denominator is the number of subjects included in the particular analysis population. [Table 11](#) will present the cumulative proportion of BV recurrence by Visit 4 (Week 12) (and 95% Wilson confidence interval) in each treatment group along with the odds ratio of BV recurrence proportions between treatment groups (and 95% asymptotic confidence interval). The p-value from the Chi-Square test will be presented. The summaries will be calculated in the ITT, mITT, CC, and PP populations, where the ITT and mITT summaries will be replicated using the imputation methods described in Section 6.5. [Listing 6](#) will present individual efficacy data for all subjects.

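### No analysis of the primary endpoint uses BV status at Visit 1, although it is measured before randomization and a case that persists counts as a recurrence

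*SAP*

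**What the plan says.** SAP 8.1 compares the cumulative proportion with recurrence by Visit 4 between arms in a 2x2 table: "The p-value from the Chi-Square test will be presented", with an unadjusted odds ratio. Protocol 11.3, 11.4 and 11.6.4.1 name the same test. SAP 6.4 lists no adjustment covariate. SAP 4.4.2 describes permuted blocks and names no stratification factor.

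Protocol 7.2 puts vaginal pH, wet mount, amine test and "Vaginal swab for Gram stain (Nugent scoring system" under item 4 of the enrollment visit, ahead of randomization (item 9) and the first dose (item 10). Women still positive then are enrolled without re-treatment.

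Under SAP 3.3.2, "A positive diagnosis of BV at the enrollment visit will not be considered a recurrence of BV", but any positive result at a later visit is, with treatment failure and new infection counted alike. SAP 3.3.4 generally takes the last value before dosing as baseline but makes an exception here: "the baseline BV diagnosis will be the diagnosis at the screening visit".

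The other planned analyses of recurrence vary the population, the imputation or the handling of re-treated women (SAP 6.5, 8.2), or break results down by race (SAP 8.3). The exploratory repeated-measures model has terms for treatment, time and their interaction only.

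**The concern.** Eligibility requires at least three Amsel criteria and a Nugent score of at least 4 at screening, so the baseline the SAP names takes one value in all eligible women and carries no prognostic information. The value that does vary, and stands closest to the start of follow-up, is collected and then used in no analysis of the endpoint. A woman who never cleared her BV enters at risk in an obvious way, because her persisting case is counted as an event at Visit 2. Protocol 2.1 also suggests, from the Phase II-a data, that BV-associated bacteria may impede both the antibiotic and the product.

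Two things could be at stake: some power in a trial of which the SAP says "this trial is powered at the 70% level", and protection of a single trial's result if the arms differ by chance in residual BV.

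**Working it through.** **Inputs from the documents.** Placebo recurrence 30%, LACTIN-V 15% (a 50% reduction), 2:1 allocation, 10% drop-out, 70% power and N = 228 (SAP 5); two-sided 5% level (SAP 6.1).

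**Reproducing 228.** The average rate is (0.30 + 2 × 0.15)/3 = 0.20. The placebo group size for Pearson's chi-square is

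n = [1.96 √(0.20 × 0.80 × 1.5) + 0.524 √(0.30 × 0.70 + 0.15 × 0.85/2)]² / 0.15² = 67.7, so 68.

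The total is 3 × 68 = 204, and 204/0.90 = 226.7, so 227; the next multiple of 3 is 228. The plan's figure stands. With 228 × 0.90 = 205 complete cases (137 and 68), power by formula is 70.4%.

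**Assumptions.** Neither the prevalence of Visit 1 BV nor its odds ratio (OR) for recurrence is in the documents, so both are varied. The marginal rates are held at 30% and 15%, with a common treatment odds ratio across the two strata.

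**Power.** Simulation, 100,000 trials per cell, unadjusted chi-square / CMH stratified by Visit 1 status, in %:

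| Prevalence | OR 1 | OR 2 | OR 4 | OR 8 |
|---|---|---|---|---|
| 10% | 70.7 / 70.5 | 70.5 / 70.6 | 70.8 / 72.2 | 70.8 / 74.9 |
| 20% | 70.5 / 70.2 | 70.4 / 70.7 | 70.6 / 73.2 | 70.6 / 77.0 |
| 30% | 70.6 / 70.2 | 70.7 / 71.1 | 70.8 / 73.7 | 70.5 / 77.4 |

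Extending to 40% prevalence and to OR 3 gives rounded changes of -0.5 to +0.5 points at OR 1-2, +1 to +3 at OR 3-4 and +4 to +7 at OR 8. With no treatment effect, rejection rates over all randomizations are 5.0-5.2% for the chi-square and 4.9-5.0% for CMH.

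**Chance imbalance.** The standard deviation of the between-arm difference in Visit 1 BV prevalence is √[p(1-p)(1/137 + 1/68)] = 0.148 √[p(1-p)]. This is 4.5 points at p = 10%, 5.9 at 20%, 6.8 at 30% and 7.3 at 40%. A difference above 10 points arises in about 3% of trials at 10% prevalence, 9-10% at 20% and 15% at 30%.

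**What such an imbalance does.** Take prevalence 20% and OR 4. Placebo recurrence is then 55.4% in women with Visit 1 BV and 23.7% in the others. With no treatment effect, a 10-point imbalance shifts the expected difference between arms by 0.10 × (0.554 - 0.237) = 3.2 points. Among simulated trials with an imbalance above 10 points:

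| | Chi-square | CMH |
|---|---|---|
| Power, excess in LACTIN-V arm | 51% | 71% |
| Power, excess in placebo arm | 88% | 74% |
| Rejection under the null | 8-10% | about 5% |

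**Which odds ratio is reported.** The marginal odds ratio is (0.15/0.85)/(0.30/0.70) = 0.41. In the same setting LACTIN-V recurrence among women without Visit 1 BV is 10.7%, so the within-stratum odds ratio is (0.107/0.893)/(0.237/0.763) = 0.39. The two differ with no imbalance at all, because odds ratios do not collapse over strata.

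**The case against.** The chi-square is the test named in the protocol, its type I error is correct over all randomizations, and the sample size was built for it. No stratification factor is named for the randomization, so the analysis leaves out no design factor. This is a screening trial deliberately set at 70% power. All of that stands, and it rules out calling the primary test an error.

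A reader might infer that precision is definitely being lost. The documents do not support this, because they give no data on how prognostic Visit 1 status is. They offer a reason for doubt: SAP 3.3.2 treats a result about two days after antibiotics as too early to judge failure. If the association is moderate, the gain is negligible.

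A reader might also infer that an imbalance would go unseen. It would not: the Table 13 shell, repeated for the other populations in Tables 14-16, has a Day 1 row by arm, and Listing 6 gives individual results. But the plan says nothing on what to do with an imbalance once displayed, and that row sits under the title of recurrence, which contradicts SAP 3.3.2.

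Finally, a reader might extend the point to site, since SAP 6.7 says "Center effects are not anticipated because treatment is self-administered" and cites central Nugent scoring but not Amsel. That does not carry. SAP 6.7 considers centre effects and gives reasons for pooling, and every diagnosis by the SAP 3.3.1 definition also needs the centrally read Nugent score. Stratifying by four equal sites changes simulated power by only about -1 to +2 points, so it can cost power.

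**Conclusion.** The point holds as a missed safeguard. The primary test is valid and N = 228 is correct. The gap is that no analysis of the primary endpoint uses a pre-randomization measurement that plausibly precedes the outcome, while the named baseline is constant among eligible women.

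The average power gain is between nothing and about 7 points, and reaches 4 or more only for a strong predictor (OR 8). The better argument is robustness: if Visit 1 status matters, a chance imbalance above 10 points can move the unadjusted result materially in either direction, while the stratified test is nearly unaffected. All of this rests on assumed prevalences and odds ratios. If the OR is 1, nothing is gained and a few tenths of a point of power are lost.

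**What to change.** Before unblinding, add to SAP 8.1, and name in SAP 6.4, a Cochran-Mantel-Haenszel test of BV recurrence by Visit 4 stratified by Visit 1 BV status (at least three Amsel criteria and Nugent 4 or more: yes or no, with missing as its own stratum). At minimum make it a named supportive analysis in the Complete Case population beside the protocol's chi-square. Report the Mantel-Haenszel risk difference as well as the odds ratio, and state that the odds ratio is conditional on stratum. Relabel the Day 1 row of Tables 13-16 as baseline status. No site-stratified analysis is needed.

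The cost is one extra analysis on data already collected, a trivial loss of power if the covariate is not prognostic, and a second odds ratio that will differ from the unadjusted one and needs a sentence of explanation. If the stratified test were to replace the primary test, that would depart from Protocol 11.3, 11.4 and 11.6.4.1 and would have to be documented and justified, for example in SAP 13.
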